#### 30 BACKGROUND AND SIGNIFICANCE

31

According to the latest estimates published by the International Diabetes Federation, 415

million adults were living with diabetes in 2015 and this number is expected to rise to
 642 million (or 1 adult in 10) by 2040 (1). This makes it likely that a good proportion of

the 8 million people who board an aircraft each day (www.iata.org) are flying with an

36 established diagnosis of diabetes. In the United States and based on diabetes prevalence

37 data, approximately 17 million leisure and 5.6 million business travelers travel with

- 38 diabetes and at least a quarter will be using insulin on a daily basis (2).
- 39

40 For insulin treated individuals planning long-haul travel (defined as a flight lasting more 41 than 6hours), consideration needs to be given to every stage of a journey from deciding

41 what to pack, choosing appropriate travel insurance, dealing with airport security,

43 anticipating consequences of late or delayed flights, preparing for the potential impact of

44 flying in a pressurized cabin on the performance of medical devices and choosing a meal

45 on board through to assessing the impact of crossing multiple times zones and jet lag on

46 insulin action and the perception of low blood glucose levels at altitude (3). Once a

47 traveler with diabetes arrives at their destination, it is advisable to plan in the event their

48 diabetes supplies are lost or stolen, as well as dealing with unfamiliar foods,

49 unaccustomed exercise, or even riding roller coasters (4). In one survey more than half of

50 travelers with diabetes reported difficulties in glucose management during their journey

51 compared to the month prior to leaving (5). In general, for insulin-treated individuals 52 around 10% of travelers on short as well as long-haul journeys experienced problems,

52 most commonly hypoglycemia during the journey or in the first 24 hours after arriving at

54 their destination (6). For long-haul travel in particular, there is evidence that most

physicians, including diabetes specialists, are uncertain about how to adjust insulin doses
for patients who travel across several time zones and some of the information provided is
described as "potentially harmful" (7). Furthermore, recent testimony from on-line

bloggers and patient forums continues to highlight specific problems related to diabetesand travel (8).

60

61 We sought to determine the real-life experiences of individuals traveling long distance

62 (across five or more time-zones) with type 1 diabetes (T1D). Members of the T1D

63 Exchange (n=503) online community (www.myglu.org) completed a 45-question survey

64 about their travel experiences flying long distance (9). The cohort was stratified by

65 duration of T1D and whether or not participants used continuous subcutaneous insulin

66 infusion (CSII) therapy and/or a continuous glucose monitor (CGM). In the last 5 years,

67 71% of participants had flown long distance. When asked about their perceived "fear of

68 flying," CSII users (with and without a CGM) reported their primary anxiety was

69 "losing supplies," while non-CSII users described concerns over "unstable blood

70 glucose (highs and lows)" (P < 0.05). In addition, 74% of participants reported more

71 hypoglycemia and/or hyperglycemia while traveling overseas and 9% had avoided

72 international travel altogether because of problems related to diabetes management.

73 Furthermore, 22% of participants had run out of insulin at some point during a trip and

74 37% reported inadequate attention in current sources of information to the

75 unpredictability of self-management needs while traveling. Especially problematic for

- 76 individuals traveling with T1D are a lack of resources adequately addressing: (a)
- protocols for emergencies while abroad, (b) how to navigate airport security, and (c)
- 78 managing basal insulin rates when crossing time zones. A strong need exists for easily
- 79 accessible, free resources for traveling with T1D that is tailored to both device use and
- 80 duration of the disease
- 81

82 Currently, there is a lack of patient-centered research evaluating the practical and 83 psychosocial aspects of travel and T1D. Few resources offer practical and easy to 84 understand travel guidance to individuals with T1D. Available sources of information 85 include publications targeting physicians and scientific researchers, online articles 86 providing generalized tips (transportation and storage of supplies, suggested 87 immunizations, diet regimens to follow, optimizing insulin dose modification across time 88 zones) and free electronic dosage calculators (10-14). For the most part these articles are 89 well written and offer sound counsel, but many guidelines are overly complicated with 90 medical jargon and complex tables describing insulin dosing adjustments. This poses a 91 problem for both patients and providers looking for simple travel advice (15). Diabetes

- also contributes to medical emergencies that affect 1 in every 614 flights (16).
- 93

94 On August 6th 2015 we launched www.DiabetesTravel.org, a free on-line resource

95 focusing exclusively on long-haul travel and diabetes. As well as providing information,

96 we have also offered a "travel calculator" to provide guidance on planning changes in the 97 timing and frequency of insulin therapy to aid discussions with diabetes teams caring for

97 timing and frequency of insulin therapy to aid discussions with diabetes teams caring to
 98 individuals with T1D. Since launch almost 25,000 users have logged on with 52%

99 coming from the US (source Google Analytics, accessed 12/15/2017). We have also

received multiple, favorable comments on social media, and this has been achieved

- 101 without marketing the site or the use of search engine optimization techniques.
- 102
- 102

# 104 RATIONALE FOR THE STUDY

105

The purpose of the proposed study is to compare insulin **Degludec U100** with insulin
 **Glargine U100** to determine the basal insulin of choice for adults with type 1 diabetes

- 108 who fly non-stop across multiple time zones. With the introduction of **Degludec** as basal
- 109 insulin for T1D and the opportunity to vary time of injection between 8 and 40 hours, the
- 110 use of **Degludec** as a basal insulin may make it easier for both people living with T1D
- 111 and diabetologists to plan long-haul travel compared to the use of existing basal insulins
- 112 when crossing multiple time zones (insulin degludec injection) (Label FDA
- 113 https://www.accessdata.fda.gov/drugsatfda\_docs/label/2016/203314s003lbl.pdf.
- 114 Accessed March 6, 2018.)
- 115

116

# 117 SPECIFIC OBJECTIVES

- 118
- 119 To compare glycemic control end points between **Deglude**c U100 versus **Glargine U100**
- as the basal insulin in a pilot study of adults with type 1 diabetes who are established on multiple deily injections (MDL) of insulin and flying long head
- 121 multiple daily injections (MDI) of insulin and flying long-haul.

#### 122 RESEARCH DESIGN AND METHODS

123 Study Hypothesis: Once daily Degludec U100 as the basal insulin will provide better 124

glycemic control for people with type 1 diabetes on multiple daily injections who are 125

traveling non-stop across multiple time zones than once daily **Glargine U100**.

126

#### 127 **Endpoints**:

128 The **Primary endpoint** will be, using continuous interstitial glucose monitoring (CGM),

129 achieved glycemic control defined as time in range (70-140 mg/dl) during the initial 24 130 hours local time (starting within 2 hours after arriving) in Newark, NJ or JFK, NY after

131 flying 9-10 hours West to East (from Honolulu, HI) and after the return journey from

132 Newark to Honolulu (flying East to West) comparing Glargine U100 versus

- 133 DegludecU100 as the basal insulin.
- 134

135 Participants will begin in Honolulu, HI (HNL), fly to Newark (EWR) or New York (JFK)

- 136 where they will stay for up to 72 hours followed by a return long-haul flight back to
- 137 Honolulu with up to 72 hours at this destination. This journey will be repeated after a 2
- 138 week period when subjects return to their original insulin treatment regimen and then
- 139 switch to the alternative basal insulin. When traveling east, the day gets shorter, so the

140 basal insulin dose given during travel needs to be adjusted (see below).

141

#### 142 Figure 1. Overview of protocol with Primary and Secondary endpoint timelines for

#### 143 assessment. This journey will be undertaken twice - once using Glargine U100 and

- 144 once using Degludec as the basal insulin.
- 145

P = Primary End Point : Time in range (70-140 mg/dl) during the initial 24 hours local time (starting within 2 hours after arriving in Newark (EWR)/ New York (JFK) from Honolulu (HNL) and after the return journey from EWR/JFK to HNL).

146 147

154

148 Secondary CGM End-Points comparing Glargine U100 and Degludec as the basal 149 insulin are based on recent consensus related to reporting of trials for artificial pancreas 150 development (17):

- 151 Time in range (70-180 mg/dl) within the first 24 hours after arriving in HNL and • 152 EWR or JFK (starting within 2 hours after arrival). 153
  - For the inflight period of time and for the 72 hours in each destination:
    - $\circ$  Mean +SD CGM glucose (mg/dl)

155	○ % CGM time <50 mg/dl
156	$\circ$ % CGM time <60 mg/dl
157	○ % CGM time <70 mg/dl
158	$\circ$ % CGM time 70–180 mg/dl
159	$\circ$ % CGM time >180 mg/dl
160	$\circ$ % CGM time >250 mg/dl
161	$\circ$ % CGM time >300 mg/dl
162	• SD and coefficient of variation of CGM values
163	• Fasting BG at 0600 local time, using CGM
164	• Additionally, new CGM BG ranges will be included as consensus guidelines
165	emerge, including but not limited to those from the 2019 Advanced Technologies
166	and Treatments for Diabetes International Consensus on Time in Range (29):
167	• % CGM time 54–69 mg/dl
168	$\circ$ % CGM time <54 mg/dl
169	
170	Secondary non-CGM derived endpoints will be (a) Fear of hypoglycemia (HFS II) (18)
171	and Hypoglycemic Confidence Scale (28), (b) Liverpool Jet-Lag Questionnaire (19), (c)
172	Salivary cortisol and melatonin and (d) Sleep duration and quality and (e) Activity
173	(ActiGraph, LLC, Florida) (20).
174	
175	
176	STUDY DESIGN
177	
177 178	This study will be an open-label, single center, pilot study randomized to either Glargine
177 178 179	This study will be an open-label, single center, pilot study randomized to either Glargine or Degludec as the basal insulin, and then a 2 week break, followed by a cross-over to the
177 178 179 180	This study will be an open-label, single center, pilot study randomized to either Glargine or Degludec as the basal insulin, and then a 2 week break, followed by a cross-over to the other insulin. The study will begin in Honolulu (airport code HNL) with each non-stop
177 178 179 180 181	This study will be an open-label, single center, pilot study randomized to either Glargine or Degludec as the basal insulin, and then a 2 week break, followed by a cross-over to the other insulin. The study will begin in Honolulu (airport code HNL) with each non-stop flight to Newark, NJ (EWR) or New York (JFK) lasting approximately 10 hours with a
177 178 179 180 181 182	This study will be an open-label, single center, pilot study randomized to either Glargine or Degludec as the basal insulin, and then a 2 week break, followed by a cross-over to the other insulin. The study will begin in Honolulu (airport code HNL) with each non-stop flight to Newark, NJ (EWR) or New York (JFK) lasting approximately 10 hours with a 5/6 hour time difference between destinations. After up to 72 hours in EWR or JFK, they
177 178 179 180 181 182 183	This study will be an open-label, single center, pilot study randomized to either Glargine or Degludec as the basal insulin, and then a 2 week break, followed by a cross-over to the other insulin. The study will begin in Honolulu (airport code HNL) with each non-stop flight to Newark, NJ (EWR) or New York (JFK) lasting approximately 10 hours with a 5/6 hour time difference between destinations. After up to 72 hours in EWR or JFK, they will return to Honolulu and spend up to 72 hours at that destination.
177 178 179 180 181 182 183 184	This study will be an open-label, single center, pilot study randomized to either Glargine or Degludec as the basal insulin, and then a 2 week break, followed by a cross-over to the other insulin. The study will begin in Honolulu (airport code HNL) with each non-stop flight to Newark, NJ (EWR) or New York (JFK) lasting approximately 10 hours with a 5/6 hour time difference between destinations. After up to 72 hours in EWR or JFK, they will return to Honolulu and spend up to 72 hours at that destination.
177 178 179 180 181 182 183 184 185	This study will be an open-label, single center, pilot study randomized to either Glargine or Degludec as the basal insulin, and then a 2 week break, followed by a cross-over to the other insulin. The study will begin in Honolulu (airport code HNL) with each non-stop flight to Newark, NJ (EWR) or New York (JFK) lasting approximately 10 hours with a 5/6 hour time difference between destinations. After up to 72 hours in EWR or JFK, they will return to Honolulu and spend up to 72 hours at that destination.
177 178 179 180 181 182 183 184 185 186	This study will be an open-label, single center, pilot study randomized to either Glargine or Degludec as the basal insulin, and then a 2 week break, followed by a cross-over to the other insulin. The study will begin in Honolulu (airport code HNL) with each non-stop flight to Newark, NJ (EWR) or New York (JFK) lasting approximately 10 hours with a 5/6 hour time difference between destinations. After up to 72 hours in EWR or JFK, they will return to Honolulu and spend up to 72 hours at that destination. Subjects will continue to use their regular meal-time fast-acting insulin. Based on our experience with open and closed loop studies in T1D, subjects will have basal insulin
177 178 179 180 181 182 183 184 185 186 187	This study will be an open-label, single center, pilot study randomized to either Glargine or Degludec as the basal insulin, and then a 2 week break, followed by a cross-over to the other insulin. The study will begin in Honolulu (airport code HNL) with each non-stop flight to Newark, NJ (EWR) or New York (JFK) lasting approximately 10 hours with a 5/6 hour time difference between destinations. After up to 72 hours in EWR or JFK, they will return to Honolulu and spend up to 72 hours at that destination. Subjects will continue to use their regular meal-time fast-acting insulin. Based on our experience with open and closed loop studies in T1D, subjects will have basal insulin optimized using CGM profiles for up to 4 weeks prior to travel (21). One month of CGM
177 178 179 180 181 182 183 184 185 186 187 188	This study will be an open-label, single center, pilot study randomized to either Glargine or Degludec as the basal insulin, and then a 2 week break, followed by a cross-over to the other insulin. The study will begin in Honolulu (airport code HNL) with each non-stop flight to Newark, NJ (EWR) or New York (JFK) lasting approximately 10 hours with a 5/6 hour time difference between destinations. After up to 72 hours in EWR or JFK, they will return to Honolulu and spend up to 72 hours at that destination. Subjects will continue to use their regular meal-time fast-acting insulin. Based on our experience with open and closed loop studies in T1D, subjects will have basal insulin optimized using CGM profiles for up to 4 weeks prior to travel (21). One month of CGM use for CGM naïve subjects is also a valid time for familiarity with this glucose
177 178 179 180 181 182 183 184 185 186 187 188 189	This study will be an open-label, single center, pilot study randomized to either Glargine or Degludec as the basal insulin, and then a 2 week break, followed by a cross-over to the other insulin. The study will begin in Honolulu (airport code HNL) with each non-stop flight to Newark, NJ (EWR) or New York (JFK) lasting approximately 10 hours with a 5/6 hour time difference between destinations. After up to 72 hours in EWR or JFK, they will return to Honolulu and spend up to 72 hours at that destination. Subjects will continue to use their regular meal-time fast-acting insulin. Based on our experience with open and closed loop studies in T1D, subjects will have basal insulin optimized using CGM profiles for up to 4 weeks prior to travel (21). One month of CGM use for CGM naïve subjects is also a valid time for familiarity with this glucose monitoring system.
177 178 179 180 181 182 183 184 185 186 187 188 189 190	This study will be an open-label, single center, pilot study randomized to either Glargine or Degludec as the basal insulin, and then a 2 week break, followed by a cross-over to the other insulin. The study will begin in Honolulu (airport code HNL) with each non-stop flight to Newark, NJ (EWR) or New York (JFK) lasting approximately 10 hours with a 5/6 hour time difference between destinations. After up to 72 hours in EWR or JFK, they will return to Honolulu and spend up to 72 hours at that destination. Subjects will continue to use their regular meal-time fast-acting insulin. Based on our experience with open and closed loop studies in T1D, subjects will have basal insulin optimized using CGM profiles for up to 4 weeks prior to travel (21). One month of CGM use for CGM naïve subjects is also a valid time for familiarity with this glucose monitoring system.
177 178 179 180 181 182 183 184 185 186 187 188 189 190 191	This study will be an open-label, single center, pilot study randomized to either Glargine or Degludec as the basal insulin, and then a 2 week break, followed by a cross-over to the other insulin. The study will begin in Honolulu (airport code HNL) with each non-stop flight to Newark, NJ (EWR) or New York (JFK) lasting approximately 10 hours with a 5/6 hour time difference between destinations. After up to 72 hours in EWR or JFK, they will return to Honolulu and spend up to 72 hours at that destination. Subjects will continue to use their regular meal-time fast-acting insulin. Based on our experience with open and closed loop studies in T1D, subjects will have basal insulin optimized using CGM profiles for up to 4 weeks prior to travel (21). One month of CGM use for CGM naïve subjects is also a valid time for familiarity with this glucose monitoring system.
177 178 179 180 181 182 183 184 185 186 187 188 189 190 191 192	This study will be an open-label, single center, pilot study randomized to either Glargine or Degludec as the basal insulin, and then a 2 week break, followed by a cross-over to the other insulin. The study will begin in Honolulu (airport code HNL) with each non-stop flight to Newark, NJ (EWR) or New York (JFK) lasting approximately 10 hours with a 5/6 hour time difference between destinations. After up to 72 hours in EWR or JFK, they will return to Honolulu and spend up to 72 hours at that destination. Subjects will continue to use their regular meal-time fast-acting insulin. Based on our experience with open and closed loop studies in T1D, subjects will have basal insulin optimized using CGM profiles for up to 4 weeks prior to travel (21). One month of CGM use for CGM naïve subjects is also a valid time for familiarity with this glucose monitoring system.
177 178 179 180 181 182 183 184 185 186 187 188 189 190 191 192 193	This study will be an open-label, single center, pilot study randomized to either Glargine or Degludec as the basal insulin, and then a 2 week break, followed by a cross-over to the other insulin. The study will begin in Honolulu (airport code HNL) with each non-stop flight to Newark, NJ (EWR) or New York (JFK) lasting approximately 10 hours with a 5/6 hour time difference between destinations. After up to 72 hours in EWR or JFK, they will return to Honolulu and spend up to 72 hours at that destination. Subjects will continue to use their regular meal-time fast-acting insulin. Based on our experience with open and closed loop studies in T1D, subjects will have basal insulin optimized using CGM profiles for up to 4 weeks prior to travel (21). One month of CGM use for CGM naïve subjects is also a valid time for familiarity with this glucose monitoring system.
177 178 179 180 181 182 183 184 185 186 187 188 189 190 191 192 193 194	This study will be an open-label, single center, pilot study randomized to either Glargine or Degludec as the basal insulin, and then a 2 week break, followed by a cross-over to the other insulin. The study will begin in Honolulu (airport code HNL) with each non-stop flight to Newark, NJ (EWR) or New York (JFK) lasting approximately 10 hours with a 5/6 hour time difference between destinations. After up to 72 hours in EWR or JFK, they will return to Honolulu and spend up to 72 hours at that destination. Subjects will continue to use their regular meal-time fast-acting insulin. Based on our experience with open and closed loop studies in T1D, subjects will have basal insulin optimized using CGM profiles for up to 4 weeks prior to travel (21). One month of CGM use for CGM naïve subjects is also a valid time for familiarity with this glucose monitoring system.
177 178 179 180 181 182 183 184 185 186 187 188 189 190 191 192 193 194 195	This study will be an open-label, single center, pilot study randomized to either Glargine or Degludec as the basal insulin, and then a 2 week break, followed by a cross-over to the other insulin. The study will begin in Honolulu (airport code HNL) with each non-stop flight to Newark, NJ (EWR) or New York (JFK) lasting approximately 10 hours with a 5/6 hour time difference between destinations. After up to 72 hours in EWR or JFK, they will return to Honolulu and spend up to 72 hours at that destination. Subjects will continue to use their regular meal-time fast-acting insulin. Based on our experience with open and closed loop studies in T1D, subjects will have basal insulin optimized using CGM profiles for up to 4 weeks prior to travel (21). One month of CGM use for CGM naïve subjects is also a valid time for familiarity with this glucose monitoring system.
177 178 179 180 181 182 183 184 185 186 187 188 189 190 191 192 193 194 195 196	This study will be an open-label, single center, pilot study randomized to either Glargine or Degludec as the basal insulin, and then a 2 week break, followed by a cross-over to the other insulin. The study will begin in Honolulu (airport code HNL) with each non-stop flight to Newark, NJ (EWR) or New York (JFK) lasting approximately 10 hours with a 5/6 hour time difference between destinations. After up to 72 hours in EWR or JFK, they will return to Honolulu and spend up to 72 hours at that destination. Subjects will continue to use their regular meal-time fast-acting insulin. Based on our experience with open and closed loop studies in T1D, subjects will have basal insulin optimized using CGM profiles for up to 4 weeks prior to travel (21). One month of CGM use for CGM naïve subjects is also a valid time for familiarity with this glucose monitoring system. This is a single center pilot study based in the United States for which we are planning to recruit adults with established T1D currently being treated with multiple daily injections of insulin (MDI). Subjects for this trial will consist of individuals based on inclusion and exclusion criteria (see below). The subjects must be willing to participate in the clinical trial as per protocol and randomized to the use of Glargine or Degludec as their basal insulin with a 2 week break period between insulins and flights.
177 178 179 180 181 182 183 184 185 186 187 188 189 190 191 192 193 194 195 196 197	This study will be an open-label, single center, pilot study randomized to either Glargine or Degludec as the basal insulin, and then a 2 week break, followed by a cross-over to the other insulin. The study will begin in Honolulu (airport code HNL) with each non-stop flight to Newark, NJ (EWR) or New York (JFK) lasting approximately 10 hours with a 5/6 hour time difference between destinations. After up to 72 hours in EWR or JFK, they will return to Honolulu and spend up to 72 hours at that destination. Subjects will continue to use their regular meal-time fast-acting insulin. Based on our experience with open and closed loop studies in T1D, subjects will have basal insulin optimized using CGM profiles for up to 4 weeks prior to travel (21). One month of CGM use for CGM naïve subjects is also a valid time for familiarity with this glucose monitoring system.

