### \*East coast city can be EWR (Newark) or JFK (John F. Kennedy)

294
-----

Screening Visit: Subjects that meet the eligibility criteria and have signed the informed
 consent will continue to the screening visit which will be performed at SDRI
 (www.sansum.org). The following screening assessments will be completed at baseline
 (pre-randomization):

299

315

- 300 Signed and dated informed consent • • HbA1c assessment either via fingerstick and DCA2000 or equivalent NGSP-301 302 certified point-of-care method, or by local laboratory Inclusion and exclusion criteria 303 • 304 Demographics (date of birth, gender, race and ethnicity) • 305 Medical history • 306 Substance use history (drinking, smoking, and drug habits) • • Concomitant medications 307 Physical examination 308 • 309 • Weight and height 310 • Vital signs will be tested including oral temperature, blood pressure and pulse 311 Urine pregnancy test for all premenopausal women who are not surgically sterile •
- Blood draw for routine blood count, HbA1c, and chemistry panel (values within 3 months prior to enrollment acceptable).
- Hypoglycemia unawareness Gold score (23).
  - Fear of hypoglycemia scale (HFS II) (18).
- Hypoglycemic Confidence Scale (28).

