368 to 72 hours in Newark or New York (Visit #5), return flight from EWR (or JFK) to 369 HNL (visit #6) and 48 hours in Honolulu (visit #7). Subjects originating in Santa 370 Barbara will travel to Honolulu and spend up to 2 days adjusting. At this point subjects 371 will begin their trip to the New York area. Subjects will base their travel plans at this 372 stage according to routine advice from their clinicians and from 373 www.diabetestravel.org. During travel U100 Glargine and Degludec and rapid acting 374 insulin will be maintained in cool storage  $(36^{\circ}F - 46^{\circ}F [2^{\circ}C - 8^{\circ}C])$  until first use using 375 a proprietary travel storage pack (e.g. Frio Cooling Pack). Once open for use insulins can 376 be used for up to 28 days. During this time they can be safely kept at room temperature 377 up to 86°F (30°C). The sponsor-investigator will ensure the availability of proper storage 378 conditions. During each flight, blood glucose meters and strips and continuous glucose 379 monitoring devices will be taken in hand luggage. All doses of insulin (basal and rapid 380 acting) and time of insulin injections will be recorded in the subject's travel diary as well 381 as sleep and meals. Subjects will perform at least 8 FS BGs during the flight. Subjects 382 who regularly use CGMs may continue their personal CGM systems. 383 384 For each flight the relevant basal insulin will be adjusted as described below. The 385 following secondary end-point measurements will be taken starting immediately before a 386 flight, during the flight, immediately after the flight, and after 48 hours at the destination 387 and immediately before the beginning of each flight: 388 389 Salivary cortisol and melatonin 390 Liverpool Jet-Lag Questionnaire. 391 Sleep and Activity (ActiGraph wGT3X-BT activity monitor) (ActiGraph, Pensacola, FL) 392 Interstitial glucose (CGM) Abbott FreeStyle Libre Pro. 393 Fingerstick blood sugar readings, approximately 8 times a day 394 395 **Crossover.** The return to home will be followed by a 2 week period where the subject 396 will return to their original insulin regimen and recover from long-haul travel. Study 397 insulin will not be provided during this time. 398 399 Visits #8 to #14. After 2 weeks, subjects will start the alternative basal insulin (Glargine 400 U100 to Degludec or Degludec to Glargine U100) and the protocol outlined above 401 repeated with the same direction of travel on the new basal insulin (Figure 3). The above 402 measurements will be repeated as before. 403 404 Visit #15 will be a final visit to return equipment and complete documentation. At time 405 of study completion, the corresponding source document will be completed with the date 406 of study exit. Any new or ongoing adverse events will also be documented. A summary 407 letter will be provided for each subject to inform their usual health care provider. 408 409 410 BASAL INSULIN ADJUSTMENTS FOR TRAVEL 411

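### The two hypoglycemia questionnaires are secondary endpoints, but the visible text schedules them only before randomization, so it provides no score on either insulin

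*Combined protocol and SAP*

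**What the plan says.** The Endpoints section gives the non-CGM secondary endpoints as five lettered items. The first holds two questionnaires: "Secondary non-CGM derived endpoints will be (a) Fear of hypoglycemia (HFS II) (18"), followed by "and Hypoglycemic Confidence Scale (28), (b) Liverpool Jet-Lag Questionnaire (19), (c") and the remaining items.

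The Screening Visit section introduces its list with "The following screening assessments will be completed at baseline" and labels that baseline as pre-randomization. The list includes "Fear of hypoglycemia scale (HFS II) (18") and "Hypoglycemic Confidence Scale (28").

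The text for Visits #4 to #7 sets out what is collected on treatment. It says that the "following secondary end-point measurements will be taken starting immediately before a" flight, and then during it, just after it and 48 hours into the stay. The items are saliva samples, the jet-lag questionnaire, sleep and activity by ActiGraph, CGM and fingersticks.

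For Visits #8 to #14, on the other insulin, the "measurements will be repeated as before". Visit #15 "will be a final visit to return equipment and complete documentation".

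**The concern.** In a randomized crossover of two basal insulins, an endpoint is useful if it is observed under each insulin. The general analysis statement in Statistical Considerations relies on paired t-tests or Wilcoxon signed-rank tests, and both need two on-treatment values per person. A score taken only before randomization describes the participant at entry and says nothing about glargine against degludec.

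These two scales are also the only named endpoints that record how participants feel about hypoglycemia. The Background gives this as part of the reason for the study: it notes a lack of research on the psychosocial side of travel with type 1 diabetes, and reports that people not using pumps worried about unstable glucose. The trial enrols people who do not use pumps.

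Scores not taken while a participant is on the assigned insulin cannot be recovered afterwards, because participants go back to their original regimen after the first trip.

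**Working it through.** No figure in the plan bears on this point. The power values in Table 1 concern the CGM primary endpoint. The check is therefore a trace of each non-CGM endpoint from the Endpoints section to the schedule.

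**Step 1. Endpoint list against the travel-phase list**

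| Item in Endpoints | Measure | In the travel-phase list? |
|---|---|---|
| (a) | HFS II and Hypoglycemic Confidence Scale | No |
| (b) | Jet-lag questionnaire | Yes |
| (c) | Salivary cortisol and melatonin | Yes |
| (d) | Sleep | Yes (ActiGraph) |
| (e) | Activity | Yes (ActiGraph) |

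Four of the five items recur. Only (a) is missing. The travel-phase list presents itself as the secondary endpoint measurements, so this looks like a specific omission rather than a shortened list.

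**Step 2. Other places where the scales could be given**

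- Visit #1 (randomization) and Visits #2 and #3 (basal optimization): the text names neither scale.
- Visits #8 to #14: these repeat the measurements of the first period, so an omission there carries over.
- Visit #15: this is described in one sentence and names no questionnaire. A score taken there would fall after both periods and could not form a glargine-degludec pair.
- Overview of Visit Procedures table: it names neither scale, but it names none of items (b) to (e) either. Its silence is not evidence and is not used here.

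**Step 3. Scheduled scores per person, per scale**

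- Before randomization: 1
- On glargine: 0
- On degludec: 0

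A paired comparison needs 1 + 1 = 2 on-treatment scores per person, and the visible text schedules 0 + 0 = 0. With 22 participants in the sample-size calculation and 25 to be recruited, the text yields 0 of 22 to 25 pairs for each scale. Change from baseline also needs at least one on-treatment score, so it is not available either.

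**Step 4. Can the screening score stand in?**

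No. Participants enter on any once-daily basal analogue. A comparison of screening scores by insulin at entry would be between persons, not randomized, and unrelated to the study trips. The plan to balance entry insulin does not change this.

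**The case against.** The strongest objection is that Figure 1 is missing from the available text. Its caption says it shows the timelines for primary and secondary endpoints, and only the legend for the primary endpoint survives. The summary-protocol graphic and the Figure 3 cited for period 2 are also unavailable. An on-treatment time point may appear in one of them, and a missing figure is not a fault of the plan. This stands, and it limits the claim to the visible text. It does not remove the problem, because a time point given only in a figure would contradict the written list that sites are to follow.

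A second objection is that the travel-phase list is tied to flights, so a questionnaire given once per period might not belong in it. That has some force. But no other text assigns the scales to a period, and the list does contain the other questionnaire among the endpoints.

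A third objection concerns weight. The trial is a pilot. Its hypothesis, primary endpoint, sample size and the secondary endpoints itemised in Statistical Considerations all concern CGM glycemia, and the two scales do not appear in that section. This also stands.

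A reader might infer that the scales are certainly never given on treatment, that the visit table confirms it, or that the trial's main comparison is compromised. The documents do not support any of these. The figures cannot be checked, the visit table lists no non-CGM secondary measure at all, and nothing about the primary inference depends on these scales.

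**Conclusion.** The point holds in a limited form. On the visible text, two named secondary endpoints have one pre-randomization score per person and none under either insulin. They therefore provide 0 of 22 to 25 pairs and no change from baseline. This is more than missing detail, because a site that follows the written schedule exactly cannot deliver these endpoints.

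The conclusion assumes that no unavailable figure gives an on-treatment time point. If one does, the finding becomes a contradiction between that figure and the travel-phase list, which still has to be resolved.

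The plan should be corrected before the travel visits, but this is not a reason to hold the trial. The loss is confined to two questionnaire comparisons in a pilot. The primary endpoint, its power and participant safety are unaffected.

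**What to change.** 1. Give both scales once in each treatment period while the participant is still on the assigned insulin, for example at Visits #7 and #14. Both visits already exist and come before the return to the original regimen or the end of the study.
2. Add both scales to the travel-phase list so that period 2 repeats them, and reconcile that list with Figure 1.
3. Keep the screening score as baseline. State that the endpoint is the paired between-insulin comparison of the two on-treatment scores.
4. Use each scale's published recall wording unchanged. Asking participants to answer only for the trip just completed may be tempting, but it would alter the scales, and the documents offer no support for doing so.

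If on-treatment collection is not intended, remove both scales from the endpoints and describe them as baseline characteristics. That requires no extra data collection.

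**Cost.** Two further administrations per person of questionnaires the site already uses, a short amendment and slightly more participant burden. The documents do not give the recall window of either scale. If it is longer than the trip, the score will also reflect the optimization weeks on the same insulin. In the visit table, the return flight falls nominally 5 − 0 = 5 weeks after the start of the first insulin and 13 − 8 = 5 weeks after the start of the second. Only a window longer than about five weeks would reach back before the assigned insulin.
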